9.3.2. Curated Data

Data abstracted by Clinical Research Nurses (CRNs) will include the following:

1. Race/Ethnicity.
2. Date of initial diagnosis of breast cancer.
3. Stage at initial diagnosis of breast cancer.
4. Modalities of treatment received at any point prior to A/MBC diagnosis (Surgery, Radiation, Chemotherapy, Hormone therapy). This variable will be collected as “Yes” or “Not Documented” for each modality. The last date of systemic therapy, including hormonal therapy, administered in the adjuvant setting prior to stage IV/MBC diagnosis will be documented, if applicable.
5. Among patients who have a record of hormone therapy prior to A/MBC diagnosis, the name(s), and start and end dates of the hormonal agents received in the adjuvant setting will be collected.

6. Status of the patient as having progressed at any point after initiation of the first hormone therapy in the adjuvant setting, prior to A/MBC diagnosis (Y/N). If yes, the date of first disease progression/recurrence following initiation of hormone therapy in the adjuvant setting will be collected.
7. Date of A/MBC diagnosis. This date defines the index date for the study, as referenced below in describing other study variables.
8. Stage at index date (IIIB, IIIC, or IV).
9. For patients documented as Stage IIIB or IIIC at index date, the date of Stage IV/metastatic diagnosis will be collected, if applicable, from the index date through the end of the record or the end of the study, whichever occurs first.
10. Sites of distant metastasis at index date, if applicable (Bone; Chest Wall; Contralateral Breast; Distant Lymph node(s); Liver; Lung; Peritoneum; Pleural nodules; Malignant pleural effusion; Skin; Brain; Undocumented; Other, Specify).
11. Disease histology (Adenoid cystic; Cribriform; Ductal; Inflammatory; Intraductal; Lobular; Medullary with lymphoid stroma; Medullary, NOS; Mucinous; Paget's disease and infiltrating; Paget's disease and intraductal; Papillary; Secretory; Squamous cell; Tubular; Undifferentiated; Undocumented, Other, specify) nearest in time to index date.
12. ER status nearest in time to index date.
13. PR status nearest in time to index date.
14. HER2 status nearest in time to index date.
15. Menopausal status (Pre, Peri, Post, UD) nearest in time to the date of, but before, index date. Date of documentation will be collected.

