9.5. Study Size

The study will include all patients (estimated 1100 –1300 patients) in the data set for the descriptive elements who meet the inclusion/exclusion criteria.

CCI

[REDACTED] The sample size of this study will be based on the actual number of eligible patients available for the study through CRN screening.

Given the inclusion criterion requiring a qualifying diagnosis of HR+/HER2- A/MBC between 2/3/2015 to 4/1/2019, and assuming data collection were to start by 12/1/2019, the average follow-up available for patients receiving Palbociclib plus AI combination therapy is therefore $((50/2) + 8) = 33$ months.

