4.1.1. Inclusion criteria

Patients must meet all of the following inclusion criteria to be eligible for inclusion in the study:

1. *Female or male sex.*
2. *Diagnosis (confirmed by clinical review) of A/MBC, defined as breast cancer at stage IIIB, stage IIIC, stage IV or identified as having distant metastasis.*
3. *Age ≥ 18 years at A/MBC diagnosis.*
4. *Initiated a CDK4/6i in combination with an AI as initial endocrine-based therapy after A/MBC diagnosis on or after 2/3/2015 and before 4/1/2019.*
 - *Note that the date of the start of the inclusion period reflects the month that the first CDK4/6i (ie, Palbociclib) received U.S. FDA approval.*
5. *Evidence of ER or PR positive disease, or absence of any indication of ER and PR negative disease closest to A/MBC diagnosis (ie, patients are eligible without affirmative indication of ER/PR+ status as long as ER/PR- indication is not present).*
6. *Evidence of HER2 negative disease, or absence of any indication of HER2 positive disease closest to A/MBC diagnosis (ie, patients are eligible without affirmative indication of HER2- status as long as HER2+ indication is not present).*

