5. ENDPOINTS AND COVARIATES

- Index date:** Date of A/MBC diagnosis.
- Observation period:** February 3, 2015 through the data cutoff date (end of data curation). Since data curation will start in November 2019, this allows patients to have a potential follow-up of at least 6 months.
- Follow-up:** Patients will be followed from the index date to the data cutoff date, or death, whichever comes first.

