5.3. Efficacy/Effectiveness Endpoint(s)

Variable	Operational definition
Real-world progression-free survival	
Time in months from the initial endocrine-based therapy to the first progression or censoring date will be calculated.
 
For the purpose of this study, lines of therapy will be defined as the following Progression-based lines, in which a disease progression must occur for a new regimen to be interpreted as a new line of therapy.
 
Event: Any death or disease progression. Disease progression is taken to have occurred when a pathology report or radiological scan indicates disease progression and/or there is a physician progress note consistent with that determination. If patients did not die or have disease progression, they were censored at their last visit date during the study period for patients with only one line of therapy.

Overall survival	
Time in months from the initial endocrine-based therapy to death due to any cause or censoring date will be calculated.
 
Event: Any death recorded in the data extract. Patients who did not die will be censored at the time of data cutoff (assuming this is the last date the SSDI is searched).

Real-world tumor response	
Real-world tumor response (rwTR) will be assessed as best overall response for each regimen received within the initial endocrine-based therapy.
 
Responses will be classified as Complete response (CR); Partial response (PR); Stable disease (SD); Progressive disease (PD); Not evaluable (NE); or Undocumented. The date of the first positive response (CR or PR) and of the best overall response for each regimen will be collected.

Response rate	
The number of patients with complete response or partial response divided by the number of patients with at least one tumor assessment while on the initial endocrine-based therapy.

PFIZER CONFIDENTIAL

Time to first positive response	Months from the start date of the initial endocrine based therapy to the date of the first positive response (CR or PR).
Duration of response	Month from the date of the first positive response (CR or PR) to the date of first PD assessment or death. Patients without a PD assessment or death are censored at the the data cutoff date.
Duration of initial endocrine-based treatment	Months from the start date of the initial endocrine-based therapy to the end date of the initial endocrine-based therapy.

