Duration of all treatment	Months from the start date of the initial endocrine-based therapy to the end date of the last line of treatment. Patients who are still receiving the initial endocrine-based therapy at the data cutoff date will be censored.
Duration of follow-up	Months from the index date to the date of death, or the data cutoff date, whichever came first. Patients who did not die will be censored at the data cutoff date

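### Duration of follow-up is counted from A/MBC diagnosis while OS and rwPFS are counted from therapy start, so it includes event-free pre-treatment time and overstates the follow-up behind those outcomes

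*SAP*

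**What the plan says.** Protocol 9.3.2 says of the A/MBC diagnosis date: "This date defines the index date for the study". SAP 5 uses it as the origin of follow-up: "Patients will be followed from the index date to the data cutoff date, or death, whichever comes first". SAP 5.3 repeats this in its entry for Duration of follow-up, which reads: "Months from the index date to the date of death, or the data cutoff date, whichever came first". Survivors are censored at data cutoff, so death is the event. SAP 7.2 analyses the variable by Kaplan-Meier, in the same paragraph as OS and rwPFS.

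The two main outcomes have a later origin. For OS: "Time in months from the initial endocrine-based therapy to death due to any cause or censoring date will be calculated". For rwPFS: "Time in months from the initial endocrine-based therapy to the first progression or censoring date will be calculated". Time to first positive response and the two treatment durations in SAP 5.3 also start at therapy.

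Inclusion criterion 4 (Protocol 9.2.1, SAP 4.1.1) admits patients who began a CDK4/6i with an AI "as initial endocrine-based therapy after A/MBC diagnosis on or after 2/3/2015 and before 4/1/2019". The calendar limits apply to starting therapy. No criterion limits how early the diagnosis may be.

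**The concern.** To be included, a patient must have lived from A/MBC diagnosis to therapy start. That interval is free of deaths by selection, and it lies before time zero for OS and rwPFS. It still counts toward Duration of follow-up.

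The interval can be long. Diagnoses before February 2015 are eligible. So are stage IIIB and IIIC diagnoses, and nothing excludes non-endocrine treatment given between diagnosis and the qualifying therapy.

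A reader who sees a length of follow-up beside the OS and rwPFS medians will use it to judge how well those medians are supported. Here it would look longer without any added information on either outcome. The reader could not correct for this, because the visible rows of Tables 2a/2b give time from initial breast cancer diagnosis to A/MBC diagnosis, but not time from A/MBC diagnosis to therapy.

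**Working it through.** **1. The plan's own figure.** Protocol 9.5 gives (50/2) + 8 = 33 months. From 2/3/2015 to 4/1/2019 is 1,518 days, and from 4/1/2019 to 12/1/2019 (the assumed start of data collection) is 244 days. With uniform accrual and 30.4375 days per month, (1,518/2 + 244)/30.4375 = 1,003/30.4375 = 32.95 months. The figure reproduces. The minimum in SAP 5 (at least 6 months, curation from November 2019) is also consistent: 4/1/2019 to 11/1/2019 is 214 days, or 7.03 months.

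**2. Which origin the 33 months has.** The dates are those that criterion 4 applies to therapy start, but Protocol 9.5 describes them as dates of diagnosis. I take 33 months as the therapy-start figure, on the reading of criterion 4. This is an assumption.

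**3. Effect of the origin on potential follow-up.** Let g be the mean gap from diagnosis to therapy start. Mean potential follow-up from the index date is 33 + g, and the overstatement is g/33. The documents give no g, so the values below are assumptions.

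**4. Effect on observed follow-up.** Assume potential follow-up uniform on 8 to 58 months from therapy start, and exponential OS with median 38.5 months, the lower end of the range in Protocol 7 (illustration only). Then λ = ln 2/38.5 = 0.0180. The share of deaths is 1 − (e^(−8λ) − e^(−58λ))/(50λ) = 1 − (0.866 − 0.352)/0.900 = 0.429. Mean observed follow-up from therapy is 0.429/λ = 23.8 months. Each index-based mean adds g, while the share of deaths stays at 43%. The two Kaplan-Meier columns come from a simulation of 400,000 patients with an exponential gap.

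| Mean gap g (months) | Mean potential follow-up | Overstatement | Mean observed follow-up | Kaplan-Meier median, death as event (as planned) | Reverse Kaplan-Meier median |
|---|---|---|---|---|---|
| 0 (therapy start) | 33 | none | 23.8 | 38.5 | 32.9 |
| 1 | 34 | 3.0% | 24.8 | 39.5 | 34.0 |
| 3 | 36 | 9.1% | 26.8 | 41.5 | 36.2 |
| 6 | 39 | 18.2% | 29.8 | 44.9 | 39.5 |
| 12 | 45 | 36.4% | 35.8 | 52.8 | 46.4 |

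With an OS median of 60.1 months, the upper end of the Protocol 7 range, mean observed follow-up is 26.6 months from therapy and 29.6 from the index date at g = 3, with 31% deaths in both.

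**5. Whether moving the origin is enough.** With the origin at therapy start, Duration of follow-up would have the same origin (therapy), event (death) and censoring (data cutoff) as OS. Its Kaplan-Meier curve would be the OS curve, and the 38.5 in the first row is simply the assumed OS median. Censoring deaths instead gives about 33 months, which is a length of follow-up. The origin still matters after that change: 32.9 from therapy against 36.2 from the index date at g = 3.

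**The case against.** The strongest defence is that a diagnosis origin has a purpose. SAP 7.2.2 assigns Duration of follow-up to objective 1b, which describes regimens from A/MBC diagnosis onward, and treatments and progressions are collected from the index date. No passage says the variable is meant to show how mature OS or rwPFS is. Tables 6 and 7 report events, censored patients and medians with confidence intervals, from which maturity can be read directly. This stands as a reason to keep a diagnosis-based duration for objective 1b. It does not remove the mismatch: the variable is defined among the effectiveness endpoints in SAP 5.3 and analysed with OS and rwPFS in SAP 7.2.

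Four stronger readings are tempting, and the documents do not support them.

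- *The plan's own follow-up figures run from therapy start.* Protocol 9.5 words its window as diagnosis dates. The 6-month figure is a minimum, which holds from either origin because diagnosis comes first. Protocol 9.5 needs reconciling, but it is not evidence for one origin.
- *Follow-up is defined in several conflicting ways.* SAP 5 and 5.3 agree with each other. The observation period opening on February 3, 2015 is a calendar window, and the OS and rwPFS origins are endpoint time zeros. A diagnosis before that window does sit awkwardly with it.
- *OS and rwPFS contain immortal time.* They start at therapy, so they do not.
- *The report would show 34, 36 or 39 months.* Those are mean potential follow-up. SAP 7.1 and 7.2 call for a Kaplan-Meier median, and SAP 5.3 ends follow-up at death.

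**Conclusion.** The mismatch is real. Followed as written, the SAP counts pre-treatment, event-free time as follow-up in an analysis placed beside OS and rwPFS. It overstates their follow-up by g for patients with a gap, and hardly at all for those treated soon after diagnosis.

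The size cannot be fixed from the documents. Mean gaps of 1, 3 or 6 months would raise mean potential follow-up from 33 to 34, 36 or 39 months (3%, 9% or 18%). This rests on the assumed gaps, on uniform accrual, on reading the Protocol 9.5 window as therapy-start dates, and on a cutoff at 12/1/2019. SAP 5 puts the cutoff at the end of curation; a later date lengthens follow-up equally from both origins and leaves g unchanged.

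No effectiveness estimate is biased by this, and the study tests no hypothesis. What is affected is how a reader interprets the follow-up figure. The change is worth making because it is cheap and because the gap is otherwise invisible.

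**What to change.** 1. In SAP 5.3, define the follow-up reported with OS and rwPFS as months from the start of initial endocrine-based therapy, estimated by reverse Kaplan-Meier: data cutoff is the event and deaths are censored. Align the Follow-up entry in SAP 5 and Figures 5a/5b. The two changes must be made together, because the origin alone would only duplicate OS.
2. Add a row to Tables 2a/2b for months from A/MBC diagnosis to start of initial endocrine-based therapy.
3. If objective 1b needs it, keep time from the index date as a separately labelled descriptive item.
4. Reconcile Protocol 9.5, which treats 2/3/2015 to 4/1/2019 as a diagnosis window, with inclusion criterion 4, which applies those dates to starting therapy. State the origin of the 33 months.

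One caution for the table note: rwPFS is censored at the last visit rather than at cutoff, so for rwPFS the new figure describes potential follow-up.

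The cost is SAP wording, a small protocol text correction and one table row. Both dates are already needed for the planned analyses. The stated follow-up becomes somewhat shorter.

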7. STATISTICAL METHODOLOGY AND STATISTICAL ANALYSES

7.1. Statistical Methods

Mean, standard deviation, median, 1st quartile, 3rd quartile, inter-quartile range, minimum, and maximum will be provided when performing descriptive analysis of continuous data. Numbers and percentages will be provided when performing descriptive analysis of categorical data.

An unadjusted Kaplan Meier curve will be drawn to illustrate each time-to-event outcome. Medians and 95% confidence intervals obtained from the Kaplan-Meier curves will be reported.

All data analysis will be executed using statistical software SAS version 9.4 or later.

PFIZER CONFIDENTIAL

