7.2. Statistical Analyses

Description of demographic, clinical, and treatment characteristics

Descriptive analyses will be conducted to evaluate the demographic, clinical, and treatment characteristics each of the study cohorts. Results will be reported in aggregate. Categorical variables (eg, ECOG performance status) will be reported as frequency and percentage. Continuous variables such as age will be reported as mean, standard deviation, median, 1st quartile, 3rd quartile, inter-quartile range, minimum, and maximum. In the case of missing observations, the number and percentage of missing values will be reported.

[figure not shown]
Description of effectiveness outcomes

For each of the study cohorts, real-world tumor response and response rate will be reported as frequency and percentage. Real-world progression-free survival, overall survival, time to first positive response, duration of response, duration of initial endocrine-based treatment, duration of all treatment, and Duration of follow-up will be assessed with the Kaplan-Meier method with 95% CIs, and summary tables of the number of events and censored patients. No covariates will be included. All missing values are excluded.

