**Table 11a. Duration of Response - All Eligible Patients**

	All Eligible Patients (N=)
Number of PD or Death, n (%)	
Number Censored, n (%)	
Kaplan-Meier Estimates of Time to Event (months)	
Median (95% CI)	

Table 11b. Duration of Response - Palbociclib + AI Patients

Repeat Table 11a for patients receiving Palbociclib with AI as initial endocrine-based therapy.

CCI

[figure not shown]
Figures

Kaplan-Meier curves for Palbociclib + AI initial endocrine therapy. Figures will contain the KM-estimated median survival and 95% confidence intervals in the legend.

Figure 1a: Real-world Progression-free Survival – All Eligible Patients

Figure 1b: Real-world Progression-free Survival – Palbociclib + AI Patients

CCI

Overall Survival – All Eligible Patients

Figure 2b: Overall Survival – Palbociclib + AI Patients

CCI

Figure 3a: Duration of Initial Endocrine-based Treatment – All Eligible Patients

Figure 3b: Duration of Initial Endocrine-based Treatment – Palbociclib + AI Patients

CCI

[figure not shown]
[figure not shown]

Figure 4a: Duration of All Treatment – All Eligible Patients

Figure 4b: Duration of All Treatment – Palbociclib + AI Patients

CCI

[figure not shown]

Figure 5a: Duration of Follow-up – All Eligible Patients

Figure 5b: Duration of Follow-up – Palbociclib + AI Patients

CCI

[figure not shown]

Figure 6a: Time to First Positive Response – All Eligible Patients

Figure 6b: Time to First Positive Response – Palbociclib + AI Patients

CCI

[figure not shown]
[figure not shown]

Figure 7a: Duration of Response – All Eligible Patients

Figure 7b: Duration of Response – Palbociclib + AI Patients

CCI

Additional figures will be generated for designated subgroup analyses.

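### Duration of follow-up is put through Kaplan-Meier with death as its only event, so Figures 5a and 5b show survival from A/MBC diagnosis in treated patients, not length of follow-up

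*SAP*

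**What the plan says.** SAP 5.3 defines duration of follow-up as "Months from the index date to the date of death, or the data cutoff date, whichever came first", and then states "Patients who did not die will be censored at the data cutoff date". The index date is the A/MBC diagnosis (SAP 5).

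SAP 7.2 names the variable in its Kaplan-Meier list: "duration of all treatment, and Duration of follow-up will be assessed with the Kaplan-Meier method with 95% CIs", together with "summary tables of the number of events and censored patients". SAP 7.1 adds "Medians and 95% confidence intervals obtained from the Kaplan-Meier curves will be reported". SAP Appendix 1 plots it as Figure 5a (all eligible patients) and Figure 5b (palbociclib + AI patients), under a general instruction for the figures: "Figures will contain the KM-estimated median survival and 95% confidence intervals in the legend".

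For comparison, overall survival in SAP 5.3 runs from the start of initial endocrine-based therapy to death from any cause, and "Patients who did not die will be censored at the time of data cutoff (assuming this is the last date the SSDI is searched").

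Neither document specifies reverse Kaplan-Meier or a direct summary of potential follow-up.

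**The concern.** The row for this variable does not name an event, but the rules leave only one. Each patient either dies or is censored at cutoff, and SAP 7.2 asks for counts of both. A programmer following the SAP would code death as 1 and survivor as 0. That is the coding for overall survival; only time zero differs.

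The Kaplan-Meier median in Figures 5a and 5b would then be all-cause survival from A/MBC diagnosis in patients who lived to start therapy. It would not say how long patients were observed. Readers use median follow-up to judge how mature OS is, and OS is part of primary Objective 2. A number that follows mortality can make follow-up look longer or shorter than it was. A result of not reached has no meaning as a length of follow-up, because cutoff minus index date is known for every patient.

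Starting the clock at the index date agrees with SAP 5 and is not in question.

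**Working it through.** **1. The two definitions side by side (SAP 5.3)**

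| | Duration of follow-up | Overall survival |
|---|---|---|
| Time zero | Index date (A/MBC diagnosis) | Start of initial endocrine-based therapy |
| Event | Death (only possibility) | Death |
| Censoring | Survivors at data cutoff | Survivors at data cutoff |
| Method (SAP 7.1, 7.2) | Kaplan-Meier, median, 95% CI | Kaplan-Meier, median, 95% CI |

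**2. The protocol's own follow-up figure**

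Protocol 9.5 gives an average available follow-up of (50/2) + 8 = 33 months. From the calendar dates, 2/3/2015 to 4/1/2019 is 49.87 months and 4/1/2019 to 12/1/2019 is 8.02 months. So 49.87/2 + 8.02 = 32.95 months, which reproduces the stated 33.

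**3. Assumptions for the illustration (not given in the documents)**

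- Treatment starts are uniform over 2/3/2015 to 4/1/2019.
- Survival from treatment start is exponential with median M.
- Observation ends only at death or cutoff.
- M is 24, 33, 38.5, 48 or 60.1 months. Protocol 7 gives an OS range of 38.5 to 60.1 months for HR+/HER2- disease, treated here as medians; the other values widen the range.
- The cutoff is 12/1/2019 (the data-collection start assumed in Protocol 9.5) or 6/1/2020. SAP 5 makes the cutoff the end of curation without dating it.
- n = 1200, within the planned 1100 to 1300, with 2000 simulated samples per case. Time runs from therapy start.

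**4. What each rule estimates**

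Under the SAP rule the curve estimates S(t) = 2^(−t/M). Its median is M if the curve falls to 0.5 within the longest potential follow-up.

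- Cutoff 12/1/2019: the longest potential follow-up is 49.87 + 8.02 = 57.89 months. At M = 60.1, S(57.89) = 2^(−57.89/60.1) = 0.513, so the median is usually not reached.
- Cutoff 6/1/2020: the tail is 14.03 months, so median potential follow-up is 49.87/2 + 14.03 = 38.97 months and the longest is 63.90. At M = 60.1, S(63.90) = 0.479, so the median is reached only near the end of the curve.

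**5. Results (months)**

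| True median survival | SAP rule, 12/1/2019 | Potential follow-up, 12/1/2019 | SAP rule, 6/1/2020 | Potential follow-up, 6/1/2020 |
|---|---|---|---|---|
| 24 | 24.0 | 33.0 | 24.0 | 39.0 |
| 33 | 33.1 | 33.0 | 33.1 | 39.0 |
| 38.5 | 38.5 | 33.0 | 38.5 | 39.0 |
| 48 | 47.9 | 33.0 | 48.0 | 39.0 |
| 60.1 | not reached in about 70% | 33.0 | 60.1; not reached in 27% | 39.0 |

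Reverse Kaplan-Meier and cutoff minus start both give the potential follow-up columns, to within 0.1 month. A repeat run with 4000 samples per case gave the same medians to within about 0.2 month, and not-reached shares at 60.1 of 70% and 29%. The 60.1 entry at 6/1/2020 counts samples that did not reach the median as infinite.

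The two measures agree only where median survival equals median potential follow-up: for M = 38.5 at a cutoff near 5/17/2020, and for M = 48 near 3/3/2021.

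**6. Time from diagnosis, as the SAP defines it**

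The gap from diagnosis to therapy is not given. A constant 3-month gap (M = 38.5, cutoff 12/1/2019) gives 41.4 months under the SAP rule against 35.9 for either alternative, so the discrepancy remains.

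If 20% of patients have a gap uniform over 0 to 36 months and the rest an exponential gap with mean 1.5 months, the SAP rule gives 44.6, reverse Kaplan-Meier 38.8 and the direct summary 37.6. Reverse Kaplan-Meier therefore runs somewhat high when gaps are long and variable. The largest excess found at that cutoff was 42.8 against 38.7, at M = 24. The direct summary is exact.

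**7. Plain summary of observed time**

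The ordinary median of months to death or cutoff also moves with survival: from 17.1 to 24.7 months (cutoff 12/1/2019) as M goes from 24 to 60.1. Dropping Kaplan-Meier alone is therefore not a full remedy.

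**The case against.** The strongest reply is that little depends on this output. SAP 7.2.2 maps it to Objective 1b, it has no table shell, and no effectiveness estimate uses it. OS maturity can still be read from the event and censoring counts in Table 7 and from the OS curve. Protocol 9.5 and SAP 5 also give planning values: 33 months on average and at least 6 months of potential follow-up. This is right and sets the weight of the point, but planning values do not replace a correctly reported median.

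Second, the large understatement needs 24-month survival, which lies below the 38.5 to 60.1 months cited for this disease. Within that range the discrepancy runs from +5.5 months (38.5 against 33.0) to not reached at a 12/1/2019 cutoff, and from −0.5 (38.5 against 39.0) to +21 (60.1 against 39.0) at 6/1/2020. The 95.1% 12-month survival cited in Protocol 7 for palbociclib + AI would, under a constant hazard, imply a median of 12 × ln 2 / ln(1/0.951) = 165.6 months. The output would then almost always be not reached: uninformative rather than plausibly wrong. These points narrow the likely size and leave the fault in place.

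Third, the 70% not reached at 60.1 months depends on counting from therapy start. It is 69% to 71% with constant gaps from diagnosis, 45% with exponential gaps of mean 3 months, and 0% to 3% when a fifth of patients have long gaps. This stands, and the share should be read as an illustration only.

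Fourth, patients had to survive to therapy, so the curve is not a clean estimate of survival from diagnosis either. That is true, and is a further reason not to publish it unlabelled.

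Finally, the legend wording is generic to all the Kaplan-Meier figures. That is fair; it is a loose instruction that happens to expose what Figure 5 would contain.

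**Conclusion.** The concern holds. As written, SAP 5.3 and 7.2 together produce a survival curve labelled as follow-up. That conclusion follows from the definitions and needs no assumption.

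The size depends on survival and on the actual cutoff, neither of which the documents fix. Under the assumptions above the planned median differs from true potential follow-up by −15 months (24.0 against 39.0) to +21 months (60.1 against 39.0). It is near zero where the two happen to coincide, and may not be reached at all. This is a reporting error in a supporting descriptive that should be corrected before analysis. It does not change the rwPFS, OS or response estimates.

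**What to change.** In SAP 5.3 and 7.2, replace the present rule by one of the following, and state which is used:

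- a direct summary of potential follow-up, cutoff minus index date, for every patient including those who died; or
- reverse Kaplan-Meier, with reaching the data cutoff as the event and death as censoring.

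The direct summary is the safer choice if gaps from diagnosis to therapy are long and variable. Any plain summary of observed time should be an addition, labelled as shortened by deaths. Reword the Figure 5 legend so that it does not present the value as median survival.

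It would also help to report the same measure from the start of initial endocrine-based therapy, since that is the OS time zero. A note should say that observation for rwPFS may be shorter, because for patients without an event "they were censored at their last visit date during the study period for patients with only one line of therapy".

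The cost is two wording edits, one date subtraction or a reversed event indicator, and one legend. No new data are needed. The reported number may rise, fall or hardly move.
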